10.2 Appendix 2: Clinical Laboratory Tests

The tests detailed in [Table 11](#) will be performed at the time points designated in the Schedule of Assessments ([Table 2](#)). Additional tests may be performed at any time during the trial as determined necessary by the investigator or required by local regulations.

Table 11 Protocol-Required Safety Laboratory Assessments

Laboratory Assessments	Parameters		
Hematology	Platelet count RBC count Hemoglobin Hematocrit MCV	WBC count with differential: Neutrophils Lymphocytes Monocytes Eosinophils Basophils	
Chemistry	BUN Creatinine Albumin Cholesterol Total HDL-C LDL-C Triglycerides	Potassium Sodium Calcium Bicarbonate Chloride Magnesium Glucose	ALT AST Alkaline phosphatase GGT CPK Total bilirubin Direct bilirubin Total protein TSH (with reflex-free T3/T4 if abnormal)
Urinalysis	Specific gravity Color	Dipstick ^a pH Glucose Protein Blood Ketones Bilirubin Urobilinogen Nitrite Leukocyte esterase	
Additional Tests	Prolactin (results will not be reported to investigative sites or other blinded personnel until the trial is unblinded). Serum pregnancy test (at screening and as needed for WOCBP). Urine dipstick pregnancy test (at all other time points as needed for WOCBP), followed by serum pregnancy test if urine dipstick test is positive. If serum CPK value is $>3 \times$ ULN, CPK reflex for isoenzymes. If serum CPK value is $>5 \times$ ULN, serum and urine myoglobin.		

Table 11 Protocol-Required Safety Laboratory Assessments

Laboratory Assessments	Parameters
Screening Tests	Urine drug screen for illicit drugs Serology (HIV, HbsAg, and HCV)

Abbreviations: AE = adverse event, ALT = alanine aminotransferase, AST = aspartate aminotransferase, BUN = blood urea nitrogen, CPK = creatine phosphokinase, eCRF = electronic case report from, GGT = gamma-glutamyl transferase, HbsAg = hepatitis B surface antigen, HCV = hepatitis C virus, HDL-C = high-density lipoprotein cholesterol, HIV = human immunodeficiency virus, LDL-C = low-density lipoprotein cholesterol, MCV = mean corpuscular volume, RBC = red blood cell, T3 = triiodothyronine, T4 = thyroxine, TSH = thyroid-stimulating hormone, ULN = upper limit of normal, WBC = white blood cell, WOCBP = women of childbearing potential.

- a. Results of the dipstick urine analysis will not be recorded on the eCRFs. Any clinically significant finding will be captured as an AE.

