5.14.5. Clinical Laboratory Assessments

Descriptive summaries of selected (quantitative) clinical laboratory results will be presented by treatment group and study visit. Laboratory values outside the normal range for each systematically collected hematology, blood chemistry, and urinalysis parameter will be identified. Each subject's hematology, blood chemistry, and quantitative urinalysis values will be flagged as "low" (below the lower limit of normal/LLN), "normal" (within the normal range), or "high" (above the upper limit of normal/ULN) relative to the normal ranges of the central laboratory. Each subject's qualitative urinalysis results will be flagged as "normal" or "abnormal". In addition, the severity of laboratory abnormality will be graded based on toxicity criteria specified in [Section 9.8](#) in reference to Common Terminology Criteria for Adverse Events (CTCAE) Version 5.0. The result of each laboratory test for individual subjects will be presented in a listing with the normal range defined by the central laboratory, the status relative to the normal range, and the toxicity grade.

Shift table will be used to summarize shifts from baseline toxicity grades to greatest (worst) treatment-emergent laboratory toxicity grade. For hematology and, blood chemistry, and quantitative urinalysis parameters that toxicity grade was not defined, a shift table for each laboratory test will be based on the shift from baseline high/normal/low status to the status of the maximum post-baseline value and the minimum post-baseline value (including test results from unscheduled visits, if any). Similarly, for qualitative urinalysis parameters, shifts from baseline normal/abnormal status to the worst post-baseline status will be summarized.

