Anemia	Hemoglobin (Hgb) <LLN - 10.0 g/dL; <LLN - 6.2 mmol/L; <LLN - 100 g/L	Hgb <10.0 - 8.0 g/dL; <6.2 - 4.9 mmol/L; <100 - 80g/L	Hgb <8.0 g/dL; <4.9 mmol/L; <80 g/L; transfusion indicated	Life-threatening consequences; urgent intervention indicated	Death
Hemoglobin Increased	Increase in > 0-2	Increase in >2-4g/dL	Increase > 4 g/DL	-	Death

Decreased Hemoglobin will have grades 1-3, with

- Grade 1 being any values from the LLN to 10 g/DL,
- Grade 2 from 8 to < 10 g/DL and
- Grade 3 < 8 g/DL

Increased Hemoglobin will not be graded.

Lab Test = CD4 Lymphocytes

CTCAE Term	Grade 1	Grade 2	Grade 3	Grade 4	Grade 5
CD4 lymphocytes decreased	<LLN - 500/mm ³ ; <LLN - 0.5 x 10 ⁹ /L	<500 - 200/mm ³ ; <0.5 - 0.2 x 10 ⁹ /L	<200 - 50/mm ³ ; <0.2 x 0.05 - 10 ⁹ /L	<50/mm ³ ; <0.05 x 10 ⁹ /L	-

Decreased CD4 count will have grades 1-4, with

- Grade 1 being any values from the LLN to 500/mm³,
- Grade 2 from <500 to 200/mm³ and
- Grade 3 from <200 to 50/mm³ and
- Grade 4 <50/mm³

Lab Test = Lymphocytes

CTCAE Term	Grade 1	Grade 2	Grade 3	Grade 4	Grade 5
Lymphocyte count decreased	<LLN - 800/mm ³ ; <LLN - 0.8 x 10 ⁹ /L	<800 - 500/mm ³ ; <0.8 - 0.5 x 10 ⁹ /L	<500 - 200/mm ³ ; <0.5 - 0.2 x 10 ⁹ /L	<200/mm ³ ; <0.2 x 10 ⁹ /L	Lymphocyte count decreased
Lymphocyte count increased	-	>4000/mm ³ - 20,000/mm ³	>20,000/mm ³	-	Lymphocyte count increased

Decreased Lymphocytes will have grades 1-4, with

- Grade 1 being any values from the LLN to 800/mm³,
- Grade 2 from <800 to 500/mm³ and
- Grade 3 from <500 to 200/mm³ and
- Grade 4 <200/mm³

Increase Lymphocytes will have grades 2 and 3 only, with

- Grade 2 from >4000 to 20,000/mm³ and
- Grade 3 >20,000/mm³

Lab Test = Neutrophils

CTCAE Term	Grade 1	Grade 2	Grade 3	Grade 4	Grade 5
Neutrophil count decreased	<LLN - 1500/mm ³ ; <LLN - 1.5 x 10 ⁹ /L	<1500 - 1000/mm ³ ; <1.5 - 1.0 x 10 ⁹ /L	<1000 - 500/mm ³ ; <1.0 - 0.5 x 10 ⁹ /L	<500/mm ³ ; <0.5 x 10 ⁹ /L	-

Neutrophils will have grades 1-4, with

- Grade 1 being any values from the LLN to 1500/mm³,
- Grade 2 from 1000 to <1500/mm³ and
- Grade 3 from 500 to <1000/mm³ and
- Grade 4 <500/mm³

Lab Test = Platelets

CTCAE Term	Grade 1	Grade 2	Grade 3	Grade 4	Grade 5
Platelet count decreased	<LLN - 75,000/mm ³ ; <LLN - 75.0 x 10 ⁹ /L	<75,000 - 50,000/mm ³ ; <75.0 - 50.0 x 10 ⁹ /L	<50,000 - 25,000/mm ³ ; <50.0 - 25.0 x 10 ⁹ /L	<25,000/mm ³ ; <25.0 x 10 ⁹ /L	-

Platelet count will not be CTCAE graded

Lab Test = WBC

CTCAE Term	Grade 1	Grade 2	Grade 3	Grade 4	Grade 5

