White blood cell decreased	<LLN - 3000/mm3; <LLN - 3.0 x 10e9 /L	<3000 - 2000/mm3; <3.0 - 2.0 x 10e9 /L	<2000 - 1000/mm3; <2.0 - 1.0 x 10e9 /L	<1000/mm3; <1.0 x 10e9 /L	-
Leukocytosis	-	-	>100,000/mm3	Clinical manifestations of leucostasis; urgent intervention indicated	Death

Decreased WBC will have grades 1-4, with

- Grade 1 being any values from the LLN to 3000/mm3,
- Grade 2 from 2000 to <3,000/mm3 and
- Grade 3 from 1000 to <2,000/mm3 and
- Grade 4 <1000/mm3

High WBC will have grade 1, with

- Grade 1 >11,000/mm3 (<https://www.aafp.org/afp/2000/1101/p2053.html>),

Lab Test = Urine Glucose

CTCAE Term	Grade 1	Grade 2	Grade 3	Grade 4	Grade 5
Glucosuria	Present	-	-	-	-

Urine Glucose will have grades 1,

- Grade 1 if not negative or trace

Lab Test = Urine Protein

CTCAE Term	Grade 1	Grade 2	Grade 3	Grade 4	Grade 5
Proteinuria	1+ proteinuria; urinary protein \geq ULN - <1.0 g/24 hrs	Adult: 2+ and 3+ proteinuria; urinary protein 1.0 - <3.5 g/24 hrs; Pediatric: Urine P/C (Protein/Creatinine) ratio 0.5 - 1.9	Adult: Urinary protein \geq 3.5 g/24 hrs; 4+ proteinuria; Pediatric: Urine P/C (Protein/Creatinine) ratio $>$ 1.9	-	-

Urine Protein will have grades 1-3, with

- Grade 1 =1+,
- Grade 2 = 2+ to 3+
- Grade 3 = 4+

Lab Test: Urine RBCs/Blood

CTCAE Term	Grade 1	Grade 2		Grade 3	Grade 4	Grade 5
Hematuria	Asymptomatic; clinical or diagnostic observations only; intervention not indicated	Symptomatic; urinary catheter or bladder irrigation indicated; limiting instrumental ADL		Gross hematuria; transfusion, IV medications, or hospitalization indicated; elective invasive intervention indicated; limiting self care ADL	Life-threatening consequences; urgent invasive intervention indicated	Death

Urine blood will not be CTCAE graded

Lab Test: eGFR or CrCl

CTCAE Term	Grade 1	Grade 2	Grade 3	Grade 4	Grade 5
eGFR decreased/CrCl decreased	eGFR (estimated Glomerular Filtration Rate) or CrCl (creatinine clearance) <LLN - 60 ml/min/1.73 m ² or proteinuria 2+ present; urine protein/creatinine >0.5	eGFR or CrCl 59 - 30 ml/min/1.73 m ²	eGFR or CrCl 29 - 15 ml/min/1.73 m ²	eGFR or CrCl <15 ml/min/1.73 m ² ; dialysis or renal transplant indicated	Death

Values will be graded using the CTCAE values noted above with Grade 1 – Grade 4 values.

eGFR/CrCl:

Grade 1: < LLN – 60 ml/min/1.73 m²

Grade 2: 30 - < 60 ml/min/1.73 m²

Grade 3: 15 - < 30 ml/min/1.73 m²

Grade 4: < 15 ml/min/1.73

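### Categorical laboratory summaries cannot separate severe from mild thrombocytopenia, or WBC above 100,000/mm3 from mild leukocytosis, although SAP 9.8 prints the numeric limits

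*SAP*

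**What the plan says.** SAP 5.14.5 states that "the severity of laboratory abnormality will be graded based on toxicity criteria specified in" Section 9.8, with CTCAE version 5.0 as the reference. Graded tests are summarised by a shift from baseline grade to worst treatment-emergent grade. Haematology tests without a defined grade get a different table: high/normal/low status at baseline against the status of the highest and lowest post-baseline values.

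SAP 3.2.4.1 counts a treatment-emergent laboratory toxicity when the grade rises by one or more from baseline.

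For most tests SAP 9.8 prints the CTCAE row and then the rule to be programmed. Under platelets, the row is numeric for Grades 1 to 4 (Grade 3 is shown as "<50,000 - 25,000/mm", in mm3), and the rule is "Platelet count will not be CTCAE graded". Under WBC, the leukocytosis row has Grade 3 above 100,000/mm3 and a clinical Grade 4 ("Clinical manifestations of leucostasis; urgent intervention indicated"). The rule is "High WBC will have grade 1, with" a single limit, "Grade 1 >11,000/mm3". For low counts the same entry reads "Decreased WBC will have grades 1-4, with" limits listed for each grade.

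Protocol Appendix 2, Table 11 lists both tests among the required haematology parameters; the platelet entry is in "Platelet count RBC count Hemoglobin Hematocrit MCV".

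**The concern.** The usual reason for leaving a CTCAE row ungraded is that its grades depend on symptoms or treatment, which a laboratory file does not hold. That explains uric acid, bicarbonate, phosphate, eosinophils and urine blood in SAP 9.8. It does not explain platelets, where all four grades can be read from the number alone. Elsewhere, when a row mixes numbers with clinical wording, the appendix generally keeps the numbers (sodium, potassium, amylase, lipase), so dropping the one numeric limit for leukocytosis is also out of line.

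At stake is what the by-arm laboratory tables can show. A worst-grade shift table exists to count, by treatment group, the subjects whose values became severe. For these two tests it cannot do so.

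**Working it through.** The plan states no figure to reproduce. The check is to apply the printed rows and the planned rules to the same values.

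**Inputs (SAP 9.8)**
- Platelets, printed row: Grade 1 below the lower limit of normal (LLN) down to 75,000/mm3; Grade 2 below 75,000 to 50,000; Grade 3 below 50,000 to 25,000; Grade 4 below 25,000.
- Platelets, planned rule: no grade, so the high/normal/low table of SAP 5.14.5 applies.
- High WBC, printed row: nothing for Grades 1 and 2; Grade 3 above 100,000/mm3; Grade 4 clinical.
- High WBC, planned rule: Grade 1 above 11,000/mm3, with no upper bound.

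**Classification**

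| Value (per mm3) | Printed row | As planned |
|---|---|---|
| Platelets 74,000 | Grade 2 | Low |
| Platelets 49,000 | Grade 3 | Low |
| Platelets 24,000 | Grade 4 | Low |
| Platelets 5,000 | Grade 4 | Low |
| WBC 11,100 | no limit printed | Grade 1 |
| WBC 50,000 | no limit printed | Grade 1 |
| WBC 100,100 | Grade 3 | Grade 1 |
| WBC 200,000 | Grade 3 | Grade 1 |

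The documents do not give the platelet LLN. The examples above need only an LLN above 75,000/mm3, which the printed Grade 1 band already presupposes. With an assumed LLN anywhere from 130,000 to 150,000/mm3, a count 1,000 below it would be Grade 1 on the printed row and Low as planned.

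**Treatment-emergent toxicity (post-baseline grade minus baseline grade, at least 1)**
- Platelets falling from 74,000 to 24,000: the printed grades give 4 − 2 = 2, which counts. As planned there is no grade to subtract, so the event cannot count, and the shift table shows Low to Low.
- WBC rising from 12,000 to 120,000: as planned 1 − 1 = 0, which does not count. With Grade 3 added, 3 − 1 = 2, which counts.
- WBC rising from normal to 120,000: as planned 1 − 0 = 1, so it counts, but in the same cell as a rise to 11,100.

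**The case against.** The strongest reply is that this is a stated choice with a provision made for it. SAP 5.14.5 uses CTCAE as a reference only and sets out a shift table for tests without a grade. Section 9.8 also reads like a general list: it includes amylase, lipase, fibrinogen, CD4 and INR, none of them in Table 11, so a printed row is no promise to grade. Platelets are not the only departure. Increased haemoglobin has a numeric row and is left ungraded, and hyperglycaemia gets one sponsor-set grade above 200 mg/dL. All of this stands: a reader might infer that the SAP contradicts itself, and it does not. What remains is an unexplained choice that costs information.

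A reader might also infer that the plan hides life-threatening values. The documents do not support that. Neither row uses the term, and the WBC limit lost is Grade 3, since Grade 4 leukocytosis cannot be assigned from a laboratory value. Severe results also reach the report by other routes:
- Every value is listed with its range and status.
- A new low platelet count still meets the separate definition of a treatment-emergent abnormality in SAP 3.2.4.1.
- Protocol Appendix 2 requires clinically significant abnormalities to be reported as adverse events, and SAP 5.14.1 tabulates those by severity and seriousness.

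It would likewise be too broad to say that no severe haematological signal can appear. Low WBC, low neutrophils and low lymphocytes keep Grades 1 to 4, and high lymphocytes reach Grade 3.

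None of these routes, however, counts subjects by platelet grade or by WBC above 100,000/mm3 in each arm. The descriptive summaries, whose minimum and maximum might show extremes, are promised only for selected tests.

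**Conclusion.** The point holds as a minor improvement to the safety tables. For platelets, four printed grades (limits 75,000, 50,000 and 25,000/mm3) become one category, and no fall can count as treatment-emergent toxicity. For high WBC, the only printed numeric grade is dropped, and a subject already above 11,000/mm3 at baseline cannot register a rise however large.

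The number of subjects affected is not known from the documents and is probably small; Protocol 2.3 reports no notable laboratory differences from placebo in earlier trials. Efficacy, type I error and sample size are unaffected. The conclusion rests on the text of SAP 9.8, 5.14.5 and 3.2.4.1, and on no particular laboratory range beyond an LLN above 75,000/mm3.

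**What to change.** In SAP 9.8:
- Replace the platelet sentence with Grade 1 from below LLN to 75,000/mm3, Grade 2 from 50,000 to below 75,000, Grade 3 from 25,000 to below 50,000, and Grade 4 below 25,000.
- For high WBC, keep Grade 1 for values above 11,000 to 100,000/mm3 and add Grade 3 above 100,000/mm3. Skipping Grade 2 follows the appendix's own practice for high magnesium (Grades 1, 3 and 4) and serum pH (Grades 1 and 3).
- Include both in the worst-grade shift table of SAP 5.14.5. Keep the high/normal/low shift for platelets as well, because the printed row covers decreases only.

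If the sponsor prefers not to grade, a sentence giving the reason would be the minimum.

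The cost is a few lines of programming on data already collected. It is cleaner before database lock, since SAP Section 6 requires later deviations from the final plan to be documented in the study report.

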9.9. EQ-5D-5L Index Cross-walk Mapping

US Value Set

Health State (5L profile)	US
11111	1.000
11112	0.876
11113	0.844
11114	0.700
11115	0.550
11121	0.861
11122	0.820
11123	0.809
11124	0.669
11125	0.524
11131	0.827
11132	0.806
11133	0.800
11134	0.661
11135	0.517
11141	0.682
11142	0.663
11143	0.659
11144	0.544
11145	0.426
11151	0.463
11152	0.450
11153	0.446
11154	0.369
11155	0.289
11211	0.888
11212	0.846
11213	0.835
11214	0.695
11215	0.550
11221	0.832
11222	0.796
11223	0.786
11224	0.654
11225	0.517
11231	0.818
11232	0.783
11233	0.774
11234	0.644
11235	0.508
11241	0.676
11242	0.647
11243	0.640
11244	0.532
11245	0.421
11251	0.463

Health State (5L profile)	US
11252	0.443
11253	0.437
11254	0.365
11255	0.289
11311	0.860
11312	0.839
11313	0.833
11314	0.694
11315	0.550
11321	0.825
11322	0.790
11323	0.781
11324	0.650
11325	0.515
11331	0.816
11332	0.778
11333	0.768
11334	0.639
11335	0.506
11341	0.675
11342	0.643
11343	0.635
11344	0.529
11345	0.419
11351	0.463
11352	0.441
11353	0.435
11354	0.363
11355	0.289
11411	0.783
11412	0.764
11413	0.759
11414	0.641
11415	0.518
11421	0.751
11422	0.721
11423	0.713
11424	0.601
11425	0.485
11431	0.742
11432	0.710
11433	0.701
11434	0.591
11435	0.477
11441	0.618
11442	0.591
11443	0.584
11444	0.490
11445	0.393
11451	0.431
11452	0.412

Health State (5L profile)	US
11453	0.406
11454	0.338
11455	0.266
11511	0.626
11512	0.613
11513	0.609
11514	0.532
11515	0.452
11521	0.599
11522	0.579
11523	0.574
11524	0.501
11525	0.425
11531	0.592
11532	0.571
11533	0.565
11534	0.493
11535	0.418
11541	0.501
11542	0.483
11543	0.478
11544	0.410
11545	0.339
11551	0.365
11552	0.352
11553	0.348
11554	0.285
11555	0.220
12111	0.854
12112	0.815
12113	0.805
12114	0.665
12115	0.520
12121	0.802
12122	0.765
12123	0.756
12124	0.623
12125	0.486
12131	0.789
12132	0.753
12133	0.743
12134	0.613
12135	0.478
12141	0.647
12142	0.617
12143	0.609
12144	0.502
12145	0.390
12151	0.433
12152	0.413
12153	0.408

Health State (5L profile)	US
12154	0.335
12155	0.259
12211	0.828
12212	0.792
12213	0.782
12214	0.650
12215	0.513
12221	0.778
12222	0.731
12223	0.719
12224	0.595
12225	0.467
12231	0.765
12232	0.716
12233	0.703
12234	0.581
12235	0.455
12241	0.630
12242	0.587
12243	0.576
12244	0.477
12245	0.374
12251	0.426
12252	0.393
12253	0.385
12254	0.320
12255	0.252
12311	0.822
12312	0.786
12313	0.776
12314	0.646
12315	0.511
12321	0.772
12322	0.723
12323	0.710
12324	0.588
12325	0.462
12331	0.759
12332	0.707
12333	0.693
12334	0.574
12335	0.449
12341	0.625
12342	0.580
12343	0.568
12344	0.471
12345	0.370
12351	0.424
12352	0.388
12353	0.379
12354	0.316

Health State (5L profile)	US
12355	0.250
12411	0.748
12412	0.717
12413	0.709
12414	0.597
12415	0.482
12421	0.703
12422	0.659
12423	0.648
12424	0.545
12425	0.438
12431	0.692
12432	0.645
12433	0.632
12434	0.531
12435	0.427
12441	0.573
12442	0.533
12443	0.522
12444	0.437
12445	0.348
12451	0.395
12452	0.364
12453	0.356
12454	0.295
12455	0.230
12511	0.596
12512	0.576
12513	0.571
12514	0.498
12515	0.422
12521	0.562
12522	0.529
12523	0.521
12524	0.456
12525	0.388
12531	0.554
12532	0.518
12533	0.508
12534	0.445
12535	0.380
12541	0.466
12542	0.437
12543	0.429
12544	0.368
12545	0.304
12551	0.335
12552	0.315
12553	0.310
12554	0.251
12555	0.190

Health State (5L profile)	US
13111	0.825
13112	0.803
13113	0.797
13114	0.658
13115	0.514
13121	0.790
13122	0.754
13123	0.745
13124	0.614
13125	0.479
13131	0.781
13132	0.742
13133	0.732
13134	0.603
13135	0.470
13141	0.640
13142	0.608
13143	0.599
13144	0.493
13145	0.383
13151	0.427
13152	0.406
13153	0.400
13154	0.328
13155	0.253
13211	0.816
13212	0.781
13213	0.771
13214	0.641
13215	0.505
13221	0.767
13222	0.718
13223	0.705
13224	0.583
13225	0.456
13231	0.755
13232	0.702
13233	0.689
13234	0.569
13235	0.444
13241	0.620
13242	0.575
13243	0.563
13244	0.466
13245	0.364
13251	0.418
13252	0.383
13253	0.374
13254	0.311
13255	0.244
13311	0.814

Health State (5L profile)	US
13312	0.775
13313	0.765
13314	0.636
13315	0.503
13321	0.761
13322	0.709
13323	0.695
13324	0.575
13325	0.451
13331	0.748
13332	0.693
13333	0.678
13334	0.560
13335	0.438
13341	0.615
13342	0.567
13343	0.554
13344	0.459
13345	0.360
13351	0.416
13352	0.378
13353	0.368
13354	0.306
13355	0.242
13411	0.740
13412	0.707
13413	0.699
13414	0.589
13415	0.474
13421	0.693
13422	0.647
13423	0.635
13424	0.533
13425	0.428
13431	0.682
13432	0.632
13433	0.619
13434	0.519
13435	0.416
13441	0.564
13442	0.521
13443	0.510
13444	0.426
13445	0.339
13451	0.387
13452	0.355
13453	0.346
13454	0.286
13455	0.223
13511	0.590
13512	0.569

Health State (5L profile)	US
13513	0.563
13514	0.491
13515	0.416
13521	0.555
13522	0.519
13523	0.510
13524	0.447
13525	0.381
13531	0.546
13532	0.507
13533	0.497
13534	0.436
13535	0.372
13541	0.459
13542	0.427
13543	0.419
13544	0.359
13545	0.297
13551	0.329
13552	0.308
13553	0.302
13554	0.244
13555	0.184
14111	0.753
14112	0.733
14113	0.728
14114	0.604
14115	0.475
14121	0.720
14122	0.688
14123	0.680
14124	0.563
14125	0.442
14131	0.712
14132	0.677
14133	0.668
14134	0.553
14135	0.434
14141	0.583
14142	0.554
14143	0.546
14144	0.450
14145	0.349
14151	0.388
14152	0.369
14153	0.364
14154	0.294
14155	0.221
14211	0.746
14212	0.715
14213	0.706

Health State (5L profile)	US
14214	0.590
14215	0.469
14221	0.701
14222	0.656
14223	0.644
14224	0.536
14225	0.423
14231	0.690
14232	0.641
14233	0.629
14234	0.523
14235	0.412
14241	0.567
14242	0.525
14243	0.514
14244	0.426
14245	0.333
14251	0.382
14252	0.350
14253	0.342
14254	0.280
14255	0.215
14311	0.745
14312	0.710
14313	0.701
14314	0.586
14315	0.467
14321	0.696
14322	0.648
14323	0.635
14324	0.529
14325	0.419
14331	0.684
14332	0.633
14333	0.619
14334	0.515
14335	0.407
14341	0.563
14342	0.518
14343	0.506
14344	0.420
14345	0.330
14351	0.380
14352	0.346
14353	0.337
14354	0.276
14355	0.213
14411	0.681
14412	0.651
14413	0.644
14414	0.544

Health State (5L profile)	US
14415	0.440
14421	0.638
14422	0.595
14423	0.584
14424	0.492
14425	0.397
14431	0.627
14432	0.581
14433	0.569
14434	0.479
14435	0.386
14441	0.517
14442	0.478
14443	0.468
14444	0.390
14445	0.310
14451	0.353
14452	0.324
14453	0.316
14454	0.257
14455	0.196
14511	0.551
14512	0.532
14513	0.527
14514	0.457
14515	0.384
14521	0.518
14522	0.486
14523	0.478
14524	0.416
14525	0.351
14531	0.510
14532	0.475
14533	0.466
14534	0.406
14535	0.343
14541	0.425
14542	0.396
14543	0.389
14544	0.331
14545	0.270
14551	0.297
14552	0.278
14553	0.273
14554	0.217
14555	0.160
15111	0.529
15112	0.516
15113	0.512
15114	0.435
15115	0.355

Health State (5L profile)	US
15121	0.503
15122	0.482
15123	0.477
15124	0.404
15125	0.328
15131	0.496
15132	0.474
15133	0.468
15134	0.396
15135	0.321
15141	0.405
15142	0.386
15143	0.381
15144	0.313
15145	0.242
15151	0.268
15152	0.255
15153	0.251
15154	0.188
15155	0.123
15211	0.529
15212	0.509
15213	0.503
15214	0.430
15215	0.354
15221	0.496
15222	0.463
15223	0.454
15224	0.389
15225	0.321
15231	0.487
15232	0.452
15233	0.442
15234	0.379
15235	0.312
15241	0.400
15242	0.370
15243	0.362
15244	0.301
15245	0.237
15251	0.268
15252	0.248
15253	0.242
15254	0.184
15255	0.123
15311	0.529
15312	0.507
15313	0.501
15314	0.429
15315	0.354
15321	0.494

Health State (5L profile)	US
15322	0.458
15323	0.449
15324	0.385
15325	0.319
15331	0.485
15332	0.446
15333	0.436
15334	0.374
15335	0.310
15341	0.398
15342	0.366
15343	0.358
15344	0.298
15345	0.235
15351	0.268
15352	0.246
15353	0.240
15354	0.183
15355	0.123
15411	0.497
15412	0.478
15413	0.472
15414	0.403
15415	0.332
15421	0.464
15422	0.434
15423	0.426
15424	0.364
15425	0.299
15431	0.456
15432	0.423
15433	0.414
15434	0.354
15435	0.291
15441	0.372
15442	0.344
15443	0.337
15444	0.279
15445	0.219
15451	0.245
15452	0.226
15453	0.221
15454	0.167
15455	0.110
15511	0.431
15512	0.418
15513	0.414
15514	0.351
15515	0.286
15521	0.404
15522	0.384

Health State (5L profile)	US
15523	0.379
15524	0.320
15525	0.260
15531	0.397
15532	0.376
15533	0.370
15534	0.313
15535	0.253
15541	0.318
15542	0.300
15543	0.295
15544	0.241
15545	0.186
15551	0.199
15552	0.186
15553	0.182
15554	0.134
15555	0.084
21111	0.880
21112	0.840
21113	0.830
21114	0.690
21115	0.544
21121	0.826
21122	0.790
21123	0.780
21124	0.648
21125	0.511
21131	0.813
21132	0.777
21133	0.768
21134	0.638
21135	0.502
21141	0.671
21142	0.641
21143	0.634
21144	0.526
21145	0.415
21151	0.457
21152	0.437
21153	0.432
21154	0.359
21155	0.283
21211	0.853
21212	0.816
21213	0.807
21214	0.675
21215	0.538
21221	0.803
21222	0.756
21223	0.744

Health State (5L profile)	US
21224	0.620
21225	0.491
21231	0.790
21232	0.741
21233	0.728
21234	0.606
21235	0.480
21241	0.655
21242	0.612
21243	0.601
21244	0.502
21245	0.398
21251	0.451
21252	0.418
21253	0.409
21254	0.344
21255	0.276
21311	0.846
21312	0.810
21313	0.801
21314	0.671
21315	0.536
21321	0.797
21322	0.748
21323	0.735
21324	0.613
21325	0.486
21331	0.785
21332	0.732
21333	0.719
21334	0.599
21335	0.474
21341	0.651
21342	0.605
21343	0.593
21344	0.495
21345	0.394
21351	0.449
21352	0.413
21353	0.404
21354	0.340
21355	0.274
21411	0.772
21412	0.741
21413	0.733
21414	0.622
21415	0.507
21421	0.728
21422	0.684
21423	0.673
21424	0.569

Health State (5L profile)	US
21425	0.462
21431	0.717
21432	0.670
21433	0.658
21434	0.556
21435	0.451
21441	0.598
21442	0.558
21443	0.547
21444	0.462
21445	0.373
21451	0.420
21452	0.389
21453	0.381
21454	0.319
21455	0.255
21511	0.620
21512	0.600
21513	0.595
21514	0.522
21515	0.446
21521	0.586
21522	0.554
21523	0.546
21524	0.480
21525	0.412
21531	0.578
21532	0.543
21533	0.534
21534	0.470
21535	0.404
21541	0.491
21542	0.462
21543	0.454
21544	0.392
21545	0.329
21551	0.359
21552	0.339
21553	0.334
21554	0.276
21555	0.215
22111	0.823
22112	0.786
22113	0.777
22114	0.645
22115	0.507
22121	0.772
22122	0.725
22123	0.713
22124	0.589
22125	0.461

Health State (5L profile)	US
22131	0.760
22132	0.710
22133	0.697
22134	0.575
22135	0.449
22141	0.624
22142	0.581
22143	0.570
22144	0.471
22145	0.368
22151	0.420
22152	0.387
22153	0.379
22154	0.314
22155	0.246
22211	0.799
22212	0.751
22213	0.739
22214	0.616
22215	0.487
22221	0.738
22222	0.678
22223	0.662
22224	0.547
22225	0.427
22231	0.723
22232	0.659
22233	0.643
22234	0.530
22235	0.412
22241	0.594
22242	0.537
22243	0.523
22244	0.432
22245	0.338
22251	0.400
22252	0.354
22253	0.342
22254	0.285
22255	0.226
22311	0.793
22312	0.743
22313	0.730
22314	0.609
22315	0.483
22321	0.729
22322	0.666
22323	0.649
22324	0.536
22325	0.419
22331	0.714

Health State (5L profile)	US
22332	0.647
22333	0.629
22334	0.518
22335	0.403
22341	0.587
22342	0.527
22343	0.511
22344	0.422
22345	0.330
22351	0.396
22352	0.346
22353	0.333
22354	0.278
22355	0.221
22411	0.724
22412	0.680
22413	0.668
22414	0.565
22415	0.459
22421	0.666
22422	0.608
22423	0.593
22424	0.498
22425	0.400
22431	0.652
22432	0.590
22433	0.574
22434	0.482
22435	0.386
22441	0.540
22442	0.485
22443	0.471
22444	0.394
22445	0.314
22451	0.372
22452	0.327
22453	0.316
22454	0.262
22455	0.207
22511	0.583
22512	0.550
22513	0.542
22514	0.477
22515	0.409
22521	0.537
22522	0.490
22523	0.478
22524	0.421
22525	0.362
22531	0.525
22532	0.475

Health State (5L profile)	US
22533	0.462
22534	0.407
22535	0.351
22541	0.444
22542	0.401
22543	0.390
22544	0.337
22545	0.282
22551	0.322
22552	0.289
22553	0.281
22554	0.230
22555	0.178
23111	0.811
23112	0.775
23113	0.766
23114	0.635
23115	0.500
23121	0.761
23122	0.712
23123	0.699
23124	0.577
23125	0.451
23131	0.749
23132	0.696
23133	0.683
23134	0.563
23135	0.439
23141	0.615
23142	0.569
23143	0.557
23144	0.460
23145	0.359
23151	0.413
23152	0.377
23153	0.368
23154	0.305
23155	0.239
23211	0.788
23212	0.738
23213	0.726
23214	0.604
23215	0.477
23221	0.725
23222	0.662
23223	0.645
23224	0.532
23225	0.414
23231	0.709
23232	0.643
23233	0.626

Health State (5L profile)	US
23234	0.514
23235	0.399
23241	0.582
23242	0.522
23243	0.507
23244	0.418
23245	0.326
23251	0.390
23252	0.341
23253	0.328
23254	0.273
23255	0.216
23311	0.782
23312	0.729
23313	0.716
23314	0.596
23315	0.472
23321	0.716
23322	0.649
23323	0.632
23324	0.521
23325	0.405
23331	0.700
23332	0.630
23333	0.611
23334	0.502
23335	0.389
23341	0.574
23342	0.511
23343	0.494
23344	0.408
23345	0.318
23351	0.385
23352	0.332
23353	0.319
23354	0.266
23355	0.211
23411	0.714
23412	0.667
23413	0.655
23414	0.554
23415	0.449
23421	0.654
23422	0.593
23423	0.577
23424	0.484
23425	0.388
23431	0.639
23432	0.574
23433	0.558
23434	0.467

Health State (5L profile)	US
23435	0.373
23441	0.528
23442	0.471
23443	0.456
23444	0.381
23445	0.303
23451	0.362
23452	0.315
23453	0.303
23454	0.251
23455	0.197
23511	0.576
23512	0.540
23513	0.531
23514	0.468
23515	0.402
23521	0.527
23522	0.477
23523	0.464
23524	0.409
23525	0.352
23531	0.515
23532	0.462
23533	0.448
23534	0.395
23535	0.340
23541	0.435
23542	0.389
23543	0.377
23544	0.325
23545	0.272
23551	0.315
23552	0.279
23553	0.270
23554	0.221
23555	0.170
24111	0.741
24112	0.709
24113	0.701
24114	0.584
24115	0.463
24121	0.695
24122	0.650
24123	0.638
24124	0.530
24125	0.418
24131	0.684
24132	0.636
24133	0.623
24134	0.517
24135	0.407

Health State (5L profile)	US
24141	0.561
24142	0.519
24143	0.508
24144	0.420
24145	0.328
24151	0.376
24152	0.344
24153	0.336
24154	0.274
24155	0.210
24211	0.722
24212	0.677
24213	0.665
24214	0.557
24215	0.444
24221	0.663
24222	0.604
24223	0.589
24224	0.489
24225	0.385
24231	0.648
24232	0.586
24233	0.570
24234	0.472
24235	0.371
24241	0.532
24242	0.477
24243	0.462
24244	0.382
24245	0.299
24251	0.357
24252	0.312
24253	0.301
24254	0.247
24255	0.191
24311	0.717
24312	0.669
24313	0.656
24314	0.550
24315	0.440
24321	0.655
24322	0.593
24323	0.577
24324	0.479
24325	0.377
24331	0.640
24332	0.574
24333	0.557
24334	0.461
24335	0.362
24341	0.525

Health State (5L profile)	US
24342	0.466
24343	0.451
24344	0.373
24345	0.292
24351	0.353
24352	0.305
24353	0.292
24354	0.240
24355	0.186
24411	0.659
24412	0.616
24413	0.604
24414	0.513
24415	0.418
24421	0.602
24422	0.545
24423	0.531
24424	0.447
24425	0.361
24431	0.588
24432	0.528
24433	0.512
24434	0.431
24435	0.347
24441	0.485
24442	0.432
24443	0.418
24444	0.349
24445	0.277
24451	0.331
24452	0.288
24453	0.277
24454	0.226
24455	0.173
24511	0.539
24512	0.507
24513	0.499
24514	0.437
24515	0.372
24521	0.494
24522	0.448
24523	0.437
24524	0.383
24525	0.327
24531	0.483
24532	0.434
24533	0.421
24534	0.369
24535	0.315
24541	0.404
24542	0.362

Health State (5L profile)	US
24543	0.351
24544	0.301
24545	0.248
24551	0.286
24552	0.254
24553	0.245
24554	0.197
24555	0.148
25111	0.523
25112	0.503
25113	0.498
25114	0.425
25115	0.349
25121	0.490
25122	0.457
25123	0.449
25124	0.383
25125	0.315
25131	0.481
25132	0.446
25133	0.437
25134	0.373
25135	0.307
25141	0.394
25142	0.365
25143	0.357
25144	0.295
25145	0.232
25151	0.262
25152	0.242
25153	0.237
25154	0.179
25155	0.118
25211	0.517
25212	0.484
25213	0.475
25214	0.410
25215	0.342
25221	0.470
25222	0.424
25223	0.412
25224	0.355
25225	0.296
25231	0.459
25232	0.409
25233	0.397
25234	0.342
25235	0.284
25241	0.377
25242	0.335
25243	0.324

Health State (5L profile)	US
25244	0.270
25245	0.215
25251	0.255
25252	0.223
25253	0.214
25254	0.164
25255	0.111
25311	0.515
25312	0.479
25313	0.470
25314	0.406
25315	0.340
25321	0.465
25322	0.416
25323	0.403
25324	0.348
25325	0.291
25331	0.453
25332	0.400
25333	0.387
25334	0.334
25335	0.279
25341	0.373
25342	0.328
25343	0.316
25344	0.264
25345	0.211
25351	0.253
25352	0.218
25353	0.209
25354	0.160
25355	0.109
25411	0.486
25412	0.455
25413	0.447
25414	0.385
25415	0.320
25421	0.441
25422	0.397
25423	0.386
25424	0.332
25425	0.276
25431	0.430
25432	0.383
25433	0.371
25434	0.319
25435	0.265
25441	0.352
25442	0.311
25443	0.301
25444	0.251

Health State (5L profile)	US
25445	0.199
25451	0.234
25452	0.203
25453	0.195
25454	0.148
25455	0.099
25511	0.425
25512	0.405
25513	0.400
25514	0.341
25515	0.280
25521	0.391
25522	0.359
25523	0.350
25524	0.299
25525	0.247
25531	0.383
25532	0.347
25533	0.338
25534	0.289
25535	0.238
25541	0.308
25542	0.278
25543	0.270
25544	0.223
25545	0.174
25551	0.194
25552	0.173
25553	0.168
25554	0.124
25555	0.078
31111	0.854
31112	0.833
31113	0.827
31114	0.688
31115	0.543
31121	0.819
31122	0.783
31123	0.774
31124	0.643
31125	0.508
31131	0.810
31132	0.771
31133	0.761
31134	0.632
31135	0.499
31141	0.669
31142	0.637
31143	0.628
31144	0.522
31145	0.412

Health State (5L profile)	US
31151	0.456
31152	0.435
31153	0.429
31154	0.357
31155	0.282
31211	0.845
31212	0.810
31213	0.801
31214	0.670
31215	0.535
31221	0.796
31222	0.748
31223	0.735
31224	0.613
31225	0.486
31231	0.784
31232	0.732
31233	0.719
31234	0.598
31235	0.473
31241	0.650
31242	0.604
31243	0.593
31244	0.495
31245	0.393
31251	0.448
31252	0.413
31253	0.403
31254	0.340
31255	0.273
31311	0.843
31312	0.804
31313	0.794
31314	0.666
31315	0.533
31321	0.791
31322	0.739
31323	0.725
31324	0.605
31325	0.480
31331	0.778
31332	0.723
31333	0.708
31334	0.590
31335	0.467
31341	0.645
31342	0.597
31343	0.584
31344	0.488
31345	0.389
31351	0.446

Health State (5L profile)	US
31352	0.407
31353	0.397
31354	0.335
31355	0.271
31411	0.769
31412	0.736
31413	0.728
31414	0.618
31415	0.504
31421	0.723
31422	0.676
31423	0.664
31424	0.563
31425	0.457
31431	0.711
31432	0.662
31433	0.649
31434	0.549
31435	0.445
31441	0.594
31442	0.551
31443	0.539
31444	0.455
31445	0.368
31451	0.417
31452	0.384
31453	0.375
31454	0.315
31455	0.252
31511	0.619
31512	0.598
31513	0.592
31514	0.520
31515	0.445
31521	0.584
31522	0.549
31523	0.540
31524	0.476
31525	0.410
31531	0.575
31532	0.537
31533	0.527
31534	0.465
31535	0.401
31541	0.488
31542	0.457
31543	0.449
31544	0.389
31545	0.326
31551	0.358
31552	0.337

Health State (5L profile)	US
31553	0.331
31554	0.274
31555	0.214
32111	0.816
32112	0.780
32113	0.770
32114	0.640
32115	0.505
32121	0.766
32122	0.716
32123	0.704
32124	0.582
32125	0.455
32131	0.753
32132	0.701
32133	0.687
32134	0.567
32135	0.443
32141	0.619
32142	0.573
32143	0.561
32144	0.464
32145	0.364
32151	0.418
32152	0.382
32153	0.372
32154	0.309
32155	0.244
32211	0.792
32212	0.743
32213	0.730
32214	0.608
32215	0.482
32221	0.729
32222	0.666
32223	0.650
32224	0.536
32225	0.419
32231	0.714
32232	0.647
32233	0.630
32234	0.518
32235	0.403
32241	0.586
32242	0.527
32243	0.511
32244	0.422
32245	0.330
32251	0.395
32252	0.346
32253	0.333

Health State (5L profile)	US
32254	0.278
32255	0.221
32311	0.786
32312	0.734
32313	0.720
32314	0.600
32315	0.476
32321	0.720
32322	0.654
32323	0.636
32324	0.525
32325	0.410
32331	0.704
32332	0.634
32333	0.616
32334	0.506
32335	0.393
32341	0.578
32342	0.515
32343	0.499
32344	0.412
32345	0.322
32351	0.389
32352	0.337
32353	0.323
32354	0.270
32355	0.215
32411	0.719
32412	0.672
32413	0.659
32414	0.558
32415	0.454
32421	0.658
32422	0.597
32423	0.581
32424	0.489
32425	0.392
32431	0.643
32432	0.579
32433	0.562
32434	0.471
32435	0.377
32441	0.533
32442	0.475
32443	0.460
32444	0.385
32445	0.307
32451	0.367
32452	0.319
32453	0.307
32454	0.255

Health State (5L profile)	US
32455	0.202
32511	0.581
32512	0.545
32513	0.535
32514	0.472
32515	0.407
32521	0.531
32522	0.482
32523	0.469
32524	0.414
32525	0.357
32531	0.519
32532	0.466
32533	0.452
32534	0.399
32535	0.344
32541	0.440
32542	0.393
32543	0.381
32544	0.330
32545	0.277
32551	0.320
32552	0.284
32553	0.274
32554	0.226
32555	0.175
33111	0.808
33112	0.769
33113	0.759
33114	0.630
33115	0.497
33121	0.755
33122	0.703
33123	0.689
33124	0.569
33125	0.445
33131	0.742
33132	0.687
33133	0.672
33134	0.554
33135	0.432
33141	0.609
33142	0.561
33143	0.548
33144	0.453
33145	0.354
33151	0.410
33152	0.371
33153	0.361
33154	0.300
33155	0.236

Health State (5L profile)	US
33211	0.782
33212	0.729
33213	0.716
33214	0.596
33215	0.471
33221	0.716
33222	0.650
33223	0.633
33224	0.521
33225	0.405
33231	0.700
33232	0.630
33233	0.612
33234	0.502
33235	0.389
33241	0.574
33242	0.511
33243	0.495
33244	0.408
33245	0.317
33251	0.384
33252	0.332
33253	0.319
33254	0.265
33255	0.210
33311	0.775
33312	0.720
33313	0.705
33314	0.587
33315	0.465
33321	0.706
33322	0.637
33323	0.619
33324	0.509
33325	0.395
33331	0.689
33332	0.616
33333	0.597
33334	0.490
33335	0.378
33341	0.565
33342	0.499
33343	0.482
33344	0.397
33345	0.309
33351	0.378
33352	0.323
33353	0.308
33354	0.257
33355	0.204
33411	0.709

Health State (5L profile)	US
33412	0.659
33413	0.646
33414	0.546
33415	0.443
33421	0.645
33422	0.581
33423	0.565
33424	0.474
33425	0.379
33431	0.630
33432	0.562
33433	0.545
33434	0.456
33435	0.363
33441	0.520
33442	0.460
33443	0.444
33444	0.371
33445	0.295
33451	0.356
33452	0.306
33453	0.293
33454	0.244
33455	0.192
33511	0.573
33512	0.534
33513	0.524
33514	0.463
33515	0.399
33521	0.521
33522	0.468
33523	0.454
33524	0.401
33525	0.346
33531	0.508
33532	0.452
33533	0.437
33534	0.386
33535	0.333
33541	0.430
33542	0.380
33543	0.368
33544	0.318
33545	0.267
33551	0.312
33552	0.273
33553	0.263
33554	0.216
33555	0.167
34111	0.739
34112	0.704

Health State (5L profile)	US
34113	0.695
34114	0.580
34115	0.461
34121	0.690
34122	0.642
34123	0.629
34124	0.523
34125	0.413
34131	0.678
34132	0.627
34133	0.613
34134	0.509
34135	0.401
34141	0.556
34142	0.512
34143	0.500
34144	0.413
34145	0.324
34151	0.374
34152	0.339
34153	0.330
34154	0.270
34155	0.207
34211	0.717
34212	0.668
34213	0.656
34214	0.550
34215	0.439
34221	0.655
34222	0.593
34223	0.577
34224	0.479
34225	0.377
34231	0.639
34232	0.574
34233	0.557
34234	0.461
34235	0.362
34241	0.525
34242	0.466
34243	0.451
34244	0.373
34245	0.291
34251	0.352
34252	0.304
34253	0.292
34254	0.240
34255	0.186
34311	0.711
34312	0.660
34313	0.646

Health State (5L profile)	US
34314	0.542
34315	0.434
34321	0.646
34322	0.581
34323	0.564
34324	0.468
34325	0.369
34331	0.630
34332	0.561
34333	0.543
34334	0.450
34335	0.352
34341	0.517
34342	0.455
34343	0.439
34344	0.363
34345	0.284
34351	0.347
34352	0.296
34353	0.282
34354	0.232
34355	0.180
34411	0.654
34412	0.608
34413	0.596
34414	0.506
34415	0.413
34421	0.594
34422	0.535
34423	0.519
34424	0.438
34425	0.353
34431	0.580
34432	0.516
34433	0.500
34434	0.421
34435	0.338
34441	0.478
34442	0.422
34443	0.407
34444	0.340
34445	0.270
34451	0.326
34452	0.280
34453	0.268
34454	0.219
34455	0.169
34511	0.537
34512	0.502
34513	0.493
34514	0.433

Health State (5L profile)	US
34515	0.370
34521	0.489
34522	0.440
34523	0.428
34524	0.375
34525	0.321
34531	0.477
34532	0.425
34533	0.411
34534	0.361
34535	0.309
34541	0.400
34542	0.354
34543	0.343
34544	0.294
34545	0.244
34551	0.283
34552	0.248
34553	0.239
34554	0.193
34555	0.145
35111	0.522
35112	0.501
35113	0.495
35114	0.423
35115	0.348
35121	0.487
35122	0.452
35123	0.443
35124	0.379
35125	0.313
35131	0.478
35132	0.440
35133	0.430
35134	0.368
35135	0.304
35141	0.391
35142	0.360
35143	0.352
35144	0.292
35145	0.229
35151	0.261
35152	0.240
35153	0.234
35154	0.177
35155	0.117
35211	0.514
35212	0.479
35213	0.469
35214	0.406
